2.3.3 Assessment of Potential Risks and Benefits

Rationale to exposing subjects to risk

- 1.) Exposure to beta-blocker: Subjects are already on beta-blocker at the time of recruitment; thus, being on beta-blocker does not explicitly add additional risk beyond usual clinical care
- 2.) Down-titration/discontinuation: Subjects will have their beta-blocker dose decreased and/or discontinued. There is limited data to support the benefits of beta-blocker in HFP EF, despite its frequent use. Moreover, beta-blocker use poses several harms in older adults including bradycardia, heart block, hypotension, dizziness, fatigue, depression, confusion, heart failure exacerbation, cerebrovascular accident, hospitalization and death. Accordingly, down-titration/discontinuation of beta-blocker may actually be safer than continuing beta-blocker, at least in some.

To mitigate the risks of down-titration/discontinuation, we will incorporate the following:

- 1.) remote monitoring protocol that includes assessments of resting heart rate and blood pressure
- 2.) telephone calls made by the research team to the subject on the day before a dose modification is planned, to instruct about the next day's dose change; the day a dose modification is planned, to confirm the dose change was made and the assess health status; and the day following dose modification, to reassess health status, where we will ascertain whether the subject is experiencing any withdrawal effects such as chest pain, tachycardia, palpitations, diaphoresis, and shortness of breath, as well as any adverse events, such as hospitalizations and/or adverse cardiovascular events, including HF exacerbation, myocardial infarction, arrhythmia, cerebrovascular accident and death; based off of subject feedback, telephone calls may be eliminated during the last 2 weeks of each period
- 3.) We will also provide a 24 hour/7 day per week hotline for subjects to call if they develop any concerning symptoms. Importantly, we will exclude subjects with other indications for beta-blocker use to maximize safety. For example, individuals with hypertrophic cardiomyopathy will be excluded, since beta-blockers have a clear benefit in this condition (and are a Class I indication).

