subject over the phone, when applicable, we will attempt contact via email. To ensure pragmatism and enhance retention, assessments will be short and subject to change per subject feedback. Based off of subject feedback, we may eliminate subject phone calls on the last two weeks of each period. To maximize compliance and retention, subjects will receive \$50 at the end of successful completion of each phase up to 4 total phases (baseline and the 4 treatment periods). They will receive an additional \$50 as a compliance bonus at the end of period 4/end of study. In total, **subjects** will receive up to \$300. We will define compliance as attending 100% of scheduled visits and completing 90% of assessments during the defined time period.

Subjects may receive reimbursement for unanticipated fees, per PI discretion.

5. Registration Procedures

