|  | In-Office visit |
|  | Conducted Remotely |
|  | Conducted via Telephone |
|  | Collected via Garmin wearable device |

⁵ Decision Making Parameters Questionnaire to consist of Decision Conflict Scale, Decision Conflict Subscales, Patient Activation Measures Survey, Shared Decision-Making Questionnaire (SDM-1-9) and Revised Patient Attitudes Towards Deprescribing (rPATD)

⁶ Telephone contact to occur the day prior to, the day of, and the day following a dose modification. Telephone calls may be eliminated per subject feedback during the last two weeks of each period.

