6.1.2 Treatment Phase

6.1.2a Daily

- Remote Monitoring
 - Remote monitoring will collect vital sign data, including blood pressure and heart rate via a free of charge remote monitoring platform already in use in the HFpEF Program. Data will be reviewed weekly. If we encounter “Red Flags”, we will call the subject to assess symptoms, and determine the need for medical attention and/or study withdrawal in consultation with the subject’s other physicians and the DSMB.
 - Red Flags are as follows:
 - Blood pressure >160/90 mmHg or <100/60 mmHg
 - Heart Rate >100 bpm or <50 bpm
- Step Count
 - Daily step count will be collected via Garmin wearable devices that will be provided to subjects during the duration of the treatment phase of the trial.

6.1.2b Weekly

- Dose modification (as described in section 3.1)
- Telephone Contact on the day prior to the dose modification, the day of the dose modification and on the day following dose modification. Telephone calls may be eliminated during the last 2 weeks of each period per subject feedback.
- Patient Reported Outcomes (PROMIS-29, PROMIS-SF 6A) via web-based surveys taken at home on tablet computers provided to each subject, over the phone, or via email – frequency/length of surveys may be decreased per subject feedback
- Interim Events History (Adverse Events/SAE) will be asked during each phone call

6.1.2.c Biweekly

- Kansas City Cardiomyopathy Questionnaire (KCCQ-12)

6.1.2d End of Periods

- Medication Inventory
- Dose Modification
- Physical Exam, including vital signs
- Central blood pressure assessment via the UScom BP+ device, when possible
- Electrocardiogram
- Six Minute Walk Test
- Cardiopulmonary Exercise Test (at the end of Period 1 and Period 2)
 - We may draw additional blood for Troponin & NT-proBNP directly after the CPET. On visits which include a CPET, the subject may have Troponin and NT-proBNP drawn twice.
- Blood Draw for Troponin & NT-proBNP
- Blood draw for future research (at end of period 1 & end of period 2 only)
- Short Physical Performance Battery
- Qualitative interview on understandability and usability of study materials
- EQ-5D VAS
- PROMIS-29
- PROMIS-SF 6A
- PROMIS-Sexual Function

- Kansas City Cardiomyopathy Questionnaire (KCCQ-12)
- Interim Events History

6.1.2e End of Intervention Visit Period

- Medication Inventory
- Dose Modification
- Physical Exam
- Central blood pressure assessment via the UScom BP+ device
- Electrocardiogram
- Six Minute Walk Test

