7.4 Dosing and Administration

We have created a down-titration schedule, where we will reduce the dose of each beta-blocker by 50% every week, a schedule used in a prior deprescribing study of antihypertensives, that included beta-blockers. This schedule accounts for a sufficient number of half-lives to ensure drug clearance and accounts for changes in receptor density and related adrenergic hypersensitivity linked to withdrawal symptoms and ADWES observed after abrupt beta-blocker cessation. Re-initiation/up-titration will be done in reverse order. Subjects will never go on a dosage higher than their usual home dose. All drugs will be administered orally. To assist subjects with dose reduction, each subject will receive pill cutters.

| Table 4: Examples of drug down-titration schedule for selected β-blockers | | | | | |
|--|---------------|---------------|---------------|---------------|-----------------|
| Examples | Week 1 | Week 2 | Week 3 | Week 4 | Week 5+6 |
| Metoprolol 200mg daily | 100mg daily | 50mg daily | 25mg daily | 12.5mg daily | Off |
| Carvedilol 50mg BID | 25mg BID | 12.5mg BID | 6.25mg BID | 3.25mg BID | Off |
| Bisoprolol 10mg daily | 5mg daily | 2.5mg daily | Off | Off | Off |
| Atenolol 100mg daily | 50mg daily | 25mg daily | 12.5mg daily | Off | Off |
| Betaxolol 20mg daily | 10mg daily | 5mg daily | 2.5mg daily | Off | Off |
| Nebivolol 40mg daily | 20mg daily | 10mg daily | 5mg daily | Off | Off |
| Nadolol 320mg daily | 160mg daily | 80mg daily | 40mg daily | Off | Off |
| Propranolol 40mg BID | 20mg BID | 10mg BID | 5mg BID | Off | Off |
| Acetbutolol 600mg BID | 300mg BID | 150mg BID | 75mg BID | Off | Off |
| Penbutolol 80mg daily | 40mg daily | 20mg daily | 10mg daily | Off | Off |
| Pindolol 30mg BID | 15mg BID | 7.5mg BID | Off | Off | Off |
| Labetalol 1200mg BID | 600mg BID | 300mg BID | 150mg BID | Off | Off |

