4. *Exercise capacity (via peak oxygen consumption during exercise).* A general linear mixed effects model will be used, comparing VO2 of the On and Off arms.
5. *Patient-reported outcomes (PROs).* A general linear mixed effects model will be used, comparing each patient-reported outcome domain (HF-specific quality of life, fatigue, depression, anxiety, sleep, physical function, social role, and pain) of the On and Off arms. The study team will analyze data from the timeframe during which BB is completely stopped (“Off” when participating in the Off-arm) and at usual dose (“Full dose” when participating in the On-arm); this will occur during weeks 5 and 6 of each Period, or the last two weeks of the period. (see Figure 1).
6. *Subject Qualitative Interviews.* Directed content analysis methods will be used to develop relevant categories and themes from interview transcript data. Coding will be conducted through the coding platform Dedoose. Transcripts will be analyzed by two team members, consulting additional members to establish consensus where needed. Inter-rater reliability between coders will be established using a Cohen's Kappa score.

To provide statistics to the subjects when sharing key outcomes, we will compare PROs between Periods A (On) and Periods B (Off) using a linear or generalized linear mixed effects model that will include the fixed effects of beta-blocker, treatment effect (A vs B), period effect (1, 2, 3, 4 etc.) and a patient-level random intercept to account for within-patient repeated measurements. The period fixed effect will estimate the effects of down-titration/up-titration and the time-dependent treatment effect will estimate On vs. off effect. We will also explore period-specific fixed effects for treatment and compare the models using Akaike Information Criterion. As an exploratory analysis, we will also test the pattern of activity as a function of time in specialized statistical models called functional data model.

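### The option to drop telephone calls in the last two weeks of a period has no exception for dose changes, so part of the withdrawal check can lapse at the step to Off for the two longest tapers

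*Combined protocol and SAP*

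**What the plan says.** Section 2.3.3 sets out how the risk of down-titration is to be reduced. One measure is a set of three calls around each dose change: one to give the instruction, one to confirm the change and ask about health, and one the next day to ask about withdrawal effects. Footnote 6 of the Schedule of Assessments (Section 6.1) gives the same rule: "Telephone contact to occur the day prior to, the day of, and the day following a dose modification".

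The option to stop calling appears in five places:

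- Section 2.3.3, on subject feedback: "telephone calls may be eliminated during the last 2 weeks of each period".
- Section 4.6: "Based off of subject feedback, we may eliminate subject phone calls on the last two weeks of each period".
- Section 6.1, footnote 6: "Telephone calls may be eliminated per subject feedback during the last two weeks of each period".
- Section 6.1.2b: "Telephone calls may be eliminated during the last 2 weeks of each period per subject feedback".
- Section 7.9, in similar words but without the subject-feedback condition.

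Section 12.4.1, item 5, places the window when it describes the analysis data: "this will occur during weeks 5 and 6 of each Period, or the last two weeks of the period".

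Table 4 in Section 7.4 has weekly dose columns, with weeks 5 and 6 combined in the last one. Two rows are still on drug in week 4 and read Off only in that last column: "Metoprolol 200mg daily | 100mg daily | 50mg daily | 25mg daily | 12.5mg daily | Off" and "Carvedilol 50mg BID | 25mg BID | 12.5mg BID | 6.25mg BID | 3.25mg BID | Off".

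**The concern.** The three calls are the only step-by-step contact that staff initiate to look for withdrawal effects. In Sections 2.3.3, 6.1 (footnote 6) and 6.1.2b they are also the only calls described, so the option to drop calls there can only refer to them. If a dose change falls at the edge of the last two weeks, the protocol allows a listed safety check to be left out at a step it was written for. For the two longest tapers that step is the one from the last dose to none.

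What may be lost is the next-day question about symptoms and, on one reading of the calendar, same-day confirmation that the drug was stopped. It is also unclear whether the weekly adverse-event question would survive. The Schedule of Assessments marks it weekly without the elimination footnote, while Section 6.1.2b says it is asked in the calls.

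**Working it through.** **Inputs.** Table 4 (Section 7.4) for the taper, Section 12.4.1 for weeks 5 and 6 as the last two weeks, and Section 2.3.3 for the three call days. With six weeks of 7 days, the window is days 29 to 42.

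**Reproducing the taper.** Weekly halving gives metoprolol 200 → 100 → 50 → 25 → 12.5 → Off. Carvedilol goes 50 → 25 → 12.5 → 6.25 → 3.125 (printed as 3.25) → Off. Both first read Off in week 5. Across the 12 rows, Off is first reached in week 3 for 2 rows, week 4 for 8 and week 5 for 2.

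**Day of the step.** Table 4 does not date the step within the week, and Section 6.1.2d lists a dose modification at the end-of-period visit. Two calendars are therefore possible:

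| Calendar | Final step to Off | Day before | Same day | Day after | Droppable |
|---|---|---|---|---|---|
| 1: step on the first day of each weekly column | day 7 × (5 − 1) + 1 = 29 | 28, kept | 29, in window | 30, in window | 2 of 3 |
| 2: first step at the previous end-of-period visit, then every 7 days | day 7 × 4 = 28 | 27, kept | 28, kept | 29, in window | 1 of 3 |

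The day-after call is exposed on both calendars. The day-before call is exposed on neither. For the other 10 rows, all three calls for the step to Off fall before day 29.

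**Size of the last down-step.** 12.5/200 = 6.25% of home dose for metoprolol; 3.25/50 = 6.5% for carvedilol.

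**Time to the next adverse-event question.** If the weekly question is kept, it comes within about 7 days. If it is asked only in the dropped calls, the next one is at the end-of-period visit: 42 − 29 = 13 days or 42 − 28 = 14 days.

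**Up-titration.** Section 7.4 says re-initiation reverses the taper; Section 3.1 says only that a low dose is started and doubled weekly. If the reversal mirrors Table 4 exactly (an assumption), metoprolol runs 12.5, 25, 50, 100, then 200 mg in week 5. The return to full dose then meets the same window. That last up-step is 100/200 = 50% of the home dose, so the 6% figure describes only the way down. The dose never exceeds the one taken at enrolment.

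**Crossover to the next period.** On calendar 1 the day-before call falls on day 42 of the current period (1 droppable call). On calendar 2 the step is on day 42, with calls on days 41 and 42 (2 droppable).

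**Calls that an exception would keep, longest taper, four six-week periods, 3 crossovers:**

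- Down-titration final steps only (2 in either arm): 2 × 2 + 3 × 1 = 7 (calendar 1) or 2 × 1 + 3 × 2 = 8 (calendar 2).
- With mirrored up-titration, Arm 1 (3 final steps): 3 × 2 + 3 × 1 = 9 or 3 × 1 + 3 × 2 = 9.
- With mirrored up-titration, Arm 2 (4 final steps): 4 × 2 + 3 × 1 = 11 or 4 × 1 + 3 × 2 = 10.

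**The case against.** The plan clearly intends the last two weeks to be a stable phase: Section 12.4.1 treats them as the time when the drug is fully stopped or at usual dose. Section 7.9 describes weekly calls about compliance, so the option has an ordinary use that has nothing to do with dose steps. It is discretionary, and four of the five places require subject feedback. In a 16-subject Stage 1 trial meant to find a pragmatic protocol, lightening the call burden is reasonable. All of this stands, and it explains why the clause exists. It does not supply the missing exception, because footnote 6 and Section 6.1.2b attach the option directly to the dose-change calls.

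A reader might infer that the step to Off would go unmonitored. The documents do not support that. The 24-hour hotline remains. Vitals are reviewed weekly, and staff call the subject on Red Flags, whose upper limits cover tachycardia and raised blood pressure. Subjects are contacted weekly about questionnaires, and called daily if they do not complete them. The end-of-period visit covers medication and adverse events. Still, the hotline depends on the subject, and the other contacts are not a next-day symptom check.

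A reader might also infer that shorter periods spread the gap to most drugs, since a period lasts up to six weeks with no stated minimum. In a five-week period (window days 22 to 35) the step itself would lie inside the window for 10 of 12 rows on calendar 1 and 2 of 12 on calendar 2, although on calendar 2 the day-after call of the eight week-4 rows would fall on day 22. No document plans such a period, and it would leave the two longest tapers on drug in week 4, against Section 12.4.1. It is not counted here.

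The crossover calls add little. The end-of-period visit already lists dose modification, medication inventory and interim events.

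**Conclusion.** The point holds as a minor safety improvement at the final titration step. As written, the protocol permits 1 of 3 calls (step on day 28) or 2 of 3 calls (step on day 29) to be dropped at the step to Off for 2 of the 12 example tapers in a six-week period. The same applies to the return to full dose if up-titration mirrors Table 4. The rows are examples, so the number affected among the 16 subjects is unknown and may be zero. The missing exception and the week-5 step to Off come straight from the text. The count of exposed calls rests on the assumed day of the step. Nothing here shows that the taper is unsafe or that the titration schedule needs to change.

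**What to change.** In Sections 2.3.3, 4.6, 6.1 (footnote 6), 6.1.2b and 7.9, add to the option: *except calls tied to a dose modification (day before, day of, day after), which are always made*. The day-before call for the first step of the next period may be replaced by the end-of-period visit when that visit gives the dose instruction.

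This is one clause in five places of an amendment, with no new procedure, staff or titration change. The downside is a few calls that subjects might have preferred to skip: for a longest-taper subject, 1 to 2 per final step. Over four six-week periods, with crossover calls included, that is 7 to 8 if only down-titration final steps count and 9 to 11 if up-titration mirrors Table 4. The total is lower where the end-of-period visit takes the place of a crossover call. Calls not tied to a dose change can still be dropped.

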3.1 Overall Design

This single site, NIH Stage I of Behavioral Intervention Development trial will extend principles of subject-centered care (a pillar of caring for older adults with MCC) to medication management by producing a broadly applicable approach (N-of-1) that can bypass the inherent limitations of randomized controlled trials which provide average treatment effects and limited data on the effects of medication for a single individual; and thereby facilitate personalized pharmacotherapy and therapeutic precision by determining the optimal therapy for the individual in the face of the inherent complexity and heterogeneity of older adults related to variability in clinical phenotype, drug metabolism, responsiveness to therapy, and health priorities.

This study will also formalize a process that can increase subject involvement and incorporate shared decision making into medication management, an important priority in cardiovascular medicine.

We will conduct N-of-1 trials using a two-arm crossover withdrawal/reversal design (On [A] vs Off [B]) with up to 4 periods. Subjects will be randomized to either Arm1/ABAB or Arm2/BABA (see Figure 1 above). After the initial period (Period 1), each subject will crossover to the other arm and continue in that arm for up to 6 weeks (Period 2). This may be repeated for two more periods for a total of 4 periods; each period will last up to 6 weeks, permitting sufficient time for up-titration and onset of drug action, and down-titration and washout. If the subject and the principal investigator make a final decision to discontinue or continue the beta-blocker at the end of a period, the end of intervention phase will begin at the end of that period visit. For the remainder of the protocol, we refer to “end of intervention” as period 4, but this can be changed based on when a final decision is made about the beta-blocker. The end of intervention visits can occur at any of the periods. The minimum number of periods will be 2 (AB or BA). If the subject wishes to collect more data, then additional periods may be added in an alternating fashion (ABAB or BABA). Accordingly, the number of periods will be an adaptive component of the protocol.

For dose reduction, we will follow a schedule that was safe in a prior deprescribing trial—50% reduction every week until Off¹. This reduction schedule will follow up-titration and down-titration outlined in section 7.4, but will also be adaptive based on subject clinical profiles and symptoms while on and off beta-blockers.

Subjects randomized to Arm 1/ABAB (starting with On[A]), will continue their home dose during Period 1. They will then crossover to Period 2, where we will begin dose reduction. The dose will be reduced by 50% each week until the subject is off of beta-blockers. At the end of period 2 visit, subjects will be given the opportunity to decide if they would like to remain on or off their beta-blocker, or if they would like to continue into period 3. If they chose to continue to period 3, they will restart beta-blocker by starting a low dose and then doubling this dose every week until reaching their

¹ Luytmes CH, Poortvliet RKE, van Geloven N, de Waal MWM, Drewes YM, Blom JW, Smidt N, Assendelft WJJ, van den Hout WB, de Ruijter W, Numans ME. Deprescribing preventive cardiovascular medication in patients with predicted low cardiovascular disease risk in general practice - the ECSTATIC study: a cluster randomized non-inferiority trial. *BMC Med*. 2018;16(1):5.

home dose. During Period 4 (last period), we will again conduct a dose reduction, reducing each dose by 50% for a week, until the subject is off of beta-blockers.

| Arm 1 | | | |
|-----------------|------------------|-------------------|-------------------|
| Week 1-6 | Week 7-12 | Week 13-18 | Week 19-24 |
| ON (A) | OFF (B) | ON (A) | OFF (B) |
| Arm 2 | | | |
| Week 1-6 | Week 7-12 | Week 13-18 | Week 19-24 |
| OFF (B) | ON (A) | OFF (B) | ON (A) |

Table 2. Design for Arm 1 & Arm 2 for a subject completing 4 six-week periods

For patients in Arm 1, the number of periods a subject will complete is dependent on their decision about continuing or discontinuing their beta-blocker at their end of period 2 or end of period 3 visit. If a subject decides they would like to continue their beta-blocker after period 2, they will complete a period 3 to allow for safe up-titration. End of period visits, including the end of intervention period, may be conducted either remotely or in person, based on subject preference and the current status of the COVID-19 pandemic. End of period and end of intervention visits conducted remotely will not have the following physical assessments associated with it: Cardiopulmonary Exercise Test, Short Physical Performance Battery, blood draw, physical assessment, six-minute walk test, and an EKG. Subjects in Arm 1/ABAB who want to stop their beta-blocker can complete their end of intervention visit at period 2 and enter follow-up.

Test, Short Physical Performance Battery, blood draw, physical assessment, six-minute walk test, and an EKG. Subjects in Arm 1/ABAB who want to stop their beta-blocker can complete their end of intervention visit at period 2 and enter follow-up.

Subjects randomized into Arm 2/BABA will start with Off[B]. Instead of abruptly stopping beta-blocker, these subjects will have their previously prescribed home beta-blocker dose reduced by 50% each week, until the subject is completely off beta-blocker. During Period 2, they will restart beta-blocker by starting a low dose and then doubling this dose every week until reaching their home dose. During Period 3, we will again conduct a dose reduction, reducing each dose by 50% for a week, until the subject is off of beta-blockers. Finally, they will restart beta-blocker by starting a low dose and then doubling this dose every week until reaching their home dose (Similar to Period 2). See Figure 1 above. Regarding patients in Arm 2, if a subject decides they would like to stop their beta-blocker after period 2, they will complete a period 3 to allow for safe down-titration. End of period visits, including the end of intervention period, may be conducted either remotely or in person, based on subject preference and the current status of the COVID-19 pandemic. End of period and end of intervention visits conducted remotely will not have the following physical assessments associated with it: Cardiopulmonary Exercise Test, Short Physical Performance Battery, blood draw, physical assessment, six-minute walk test, and an EKG. Subjects in Arm 2/BABA who want to continue their beta-blocker can complete their end of intervention visit at period 2 and enter follow-up.

We will incorporate an adaptive study design, where each subject will have the option to participate in less (2-3) or more periods (5-6) depending on whether they need additional information to make an informed decision about continuing or discontinuing their beta-blocker at the end of this trial.

Subjects will wear a Garmin wearable device for the duration of the study to collect data on step count to quantify physical activity. We may collect additional data that is captured by the wearable devices, such as floors climbed, distance traveled and calories burned. We may eliminate the use of wearable devices per subject feedback.

Subjects will also undergo a non-invasive cardiopulmonary exercise test (CPET) at the end of period 1 and at the end of period 2 to assess exercise parameters including peak oxygen consumption. In

addition, they will undergo the short physical performance battery at baseline and at the end of each intervention period. The study team will discuss the components of the CPET with the subjects prior to their end of period visits.

Through a pre-existing remote monitoring program at Weill Cornell Medicine, we will provide subjects with a computer tablet and blood pressure cuff free-of-charge. This will allow us to collect vital sign data, including blood pressure and heart rate. We will encourage subjects to collect data up to 3 times per week. Based on patient reports of any concerning symptomatology, we may encourage increased frequency of assessments at different time points of the study. Also, based on prior experience, some subjects may want to collect data more frequently, which will allow. This approach was developed based on our preliminary data from 9 prior N-of-1 trials, where there were no serious adverse events and based on subject feedback (Several subjects requested reduced frequency of required vital sign assessment). If we encounter “Red Flags” (Table 3), we will call the subject to assess symptoms and determine the need for medical attention and/or study withdrawal.

Table 3. Red Flags triggering phone call

| | Upper Limit | Lower Limit |
|--------------------|--------------------|--------------------|
| Blood Pressure | >160/90 mmHg | <100/60 mmHg |
| Resting Heart Rate | >100 bpm | <60 bpm |

Remote monitoring will occur on a daily basis. Subjects will be provided with a tablet computer and blood pressure cuff free-of-charge. These data will be automatically uploaded to an online portal, which we will review weekly.

Subjects will complete subject-reported outcome questionnaires on quality of life, cognitive function, and sexual function at regular intervals set by each of the validated instruments during the intervention stage via their tablet computers, over the phone, or via email.

The interventions in this study will be used for either exploratory purposes or integrated with study visits to help subjects make decisions on whether they would like to continue or discontinue their beta-blocker medications. CPET and the respective results, RPM vitals (including blood pressure and heart rate), collected blood biomarker levels, step count analysis, and 6-minute walk test results and analysis will serve as exploratory measurements. Therefore, these results and values will not be explicitly shared with the subjects throughout the study to minimize bias. This way, subjects can base their decision-making on how they truly felt (measured by symptom and decision-making questionnaires) and their ability to make an informed decision with their provider. PROs, or subject reported outcomes will be included in the consenting process and study visits. These PROs include answers to their questionnaires and data visualizations analyzing how their answers differed between periods. The PROs will be explicitly discussed with the subjects to further motivate them to make an informed decision on how they feel. These expectations on what will be provided throughout the study will be clearly outlined during the consent process and baseline visit. If subjects specifically request to see these values, the PI and study team will consider providing these results for clinical purposes and per standard of care.

We will also conduct brief qualitative interviews to assess the understandability and usability of materials at each of the following time points: 1) completion of informed consent, 2) completion of each period of the intervention arms, 3) completion of the full intervention phase for each subject, and 4) at 6, 9, and 12-month post end of intervention follow-up periods. Interviews may be conducted via phone call or via Zoom, based on subject preference. The study team will audio record

these interviews. All qualitative interviews will be transcribed by a professional transcribing service. Names and all other PHI that appear in the transcription will be replaced with a generic participant ID or redacted. Additional interviews may be conducted to elicit additional information related to themes previously discussed during interviews and/or feedback provided to the study team during the course of the study.

Per subject feedback, we may eliminate the use of wearable devices or modify subject reported outcome questionnaires. We may also give caregivers the opportunity to share any feedback they may have. We will ask the subjects for permission to discuss the study with their caregivers. We will also ask the subjects for permission to contact and discuss the trial with their primary care provider or their primary cardiologist.

At the conclusion of the intervention phase, and possibly at the end of each intervention period, we will provide subjects with visual analogies of their physical function and subject reported outcomes data. These data will be discussed with them to help them determine if they would like to continue or discontinue their beta-blockers for the foreseeable future.

